7.4.11 Concomitant Medications and Procedures

Medications used by the patient and therapeutic procedures completed by the patient will be recorded in the eCRF from screening through 30 days after the last dose of study medication. See Section 6.5 and Section 6.6 for a list of medications and therapies that are prohibited and/or allowed during study treatment.

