		Screening ^a	Enrollment	Cycle 1 (21-Day Cycle)			Cycle 2 (21-Day Cycle)	Cycle 3-16 (21-Day Cycle)		EOT/ET	PTFU ^b	
	Cycle (C) Day (D) Visit Window	-28 to D1	Within 72 hours of first dose	C1 D1	C1 D2 & 4	C1 D3 & 5	C2 D1	Cx D1	Cx D16- 21	30 days (±2 days) after last dose	Minimum of 24 months	
Baseline	Informed consent	X	Randomization to Study Treatment Arm Arm 1 - brentuximab vedotin or Arm 2 - Methotrexate or Bexarotene									
	Inclusion/exclusion	X										
	Demographics	X										
	Medical history	X										
	Complete physical exam	X										
	Height	X										
	Weight ^c	X		X				X	X		X	
	Pregnancy test ^d	X		X				X	X			
Archived tissue ^e	X											
Safety Assessments	Vital signs ^f	X		X ^f				X	X		X	
	Physical exam including focused lymphoma assessment			X ^g				X	X		X	X
	ECOG performance status	X		X				X	X		X	
	Hematology/serum chemistry ^h	X						X	X		X	
	Urinalysis	X										
	12-lead ECG	X		X ⁱ								
	Immune reconstitution assessment ^l		X				X	X		X		
Disease Assessment	mSWAT and photography ^k	X	X				X	X	X	X	X	
	Circulating Sézary cells	X	X ^l					X ^l		X	X	
	FDG-PET ^m	X										
	CT ⁿ	X							X ⁿ	X ⁿ	X ⁿ	
	Quality of life assessments ^o		X				X	X		X	X	

Brentuximab vedotin (SGN-35)
Clinical Study Protocol C25001 Amendment 5, EudraCT: 2010-024215-14

	Cycle (C) Day (D) Visit Window	Screening ^a -28 to D1	Enrollment Within 72 hours of first dose	Cycle 1 (21-Day Cycle)			Cycle 2 (21-Day Cycle)	Cycle 3-16 (21-Day Cycle)		EOT/ET 30 days (±2 days) after last dose	PTFU ^b Minimum of 24 months	
				C1 D1	C1 D2 & 4	C1 D3 & 5	C2 D1	Cx D1	Cx D16- 21			
	Healthcare Utilization	X		X			X	X		X	X	
	Skin biopsy ^p (CD30 Expression)	X							X ^p	X ^p	X ^p	
	Biopsies for disease assessment ^q			X								
	Disease status/survival ^r								X	X	X	
Treatment	Brentuximab vedotin administration			X			X	X				
	Methotrexate administration ^s			X			X	X				
	Bexarotene administration ^t			Bexarotene is dosed once a day for the course of the study								
	Monitoring of concomitant medications and procedures		Recorded from screening through 30 days after the last dose of study drug.									
	Adverse event reporting ^u		Recorded from first dose of study drug through 30 days after the last dose of study drug.									
	Serious adverse events		Serious adverse events ^v will be collected from signing of the informed consent form through 30 days after the last dose of study drug									
PK/PD	PK sample ^w			X ^w	X ^w	X ^w		X ^w		X		
	CCI											

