4.3 Duration of Study

Patients who achieve a response (CR or PR) may receive brentuximab vedotin up to 16 cycles (48 weeks) or reference therapy for up to 48 weeks. Patients with stable disease may continue therapy (maximum 16 cycles brentuximab vedotin or 48 weeks reference therapy) at the discretion of the investigator. For all patients who complete either 48 weeks of dosing in the control arm or 16 cycles of brentuximab vedotin, an attempt to discontinue therapy should be made following EOT. For patients who complete 48 weeks of reference therapy, initiation of subsequent standard-of-care therapy should be discussed with the study sponsor. For patients who complete 16 cycles of brentuximab vedotin, access to brentuximab vedotin may be permitted in accordance with local regulatory requirements and at the joint discretion of the sponsor and investigator.

To permit the detection of any delayed treatment-related AEs, patients will be followed for 30 days after the last dose of study medication. Posttreatment assessments of disease response will be conducted every 12 weeks for a minimum of 24 months after EOT, and then every 6 months; or until progressive disease or study closure. All randomized patients will also be followed for survival every 12 weeks for a minimum of 24 months after the

Brentuximab vedotin (SGN-35)**Clinical Study Protocol C25001 Amendment 5, EudraCT: 2010-024215-14**

EOT visit, then every 6 months until patient withdrawal, death, or study closure.

Information may be collected by phone for patients with progressive disease.

The final analyses for the clinical study report will be performed 10 months after the last patient is enrolled (ie, approximately 34 months from the start of study). The updated analyses on the efficacy endpoints will be conducted after all patients enrolled in the study have had the opportunity to complete 16 cycles of treatment with brentuximab vedotin or 48 weeks of treatment with reference therapy and 24 months of posttreatment follow up, and will be included in an addendum to the clinical study report.

The total study duration will be approximately 5 years, including an anticipated enrollment duration of 24 months.

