7.8 Withdrawal of Patients From Study

A patient may be discontinued from the study (during treatment cycle or follow-up) for any of the following reasons:

- Lost to follow-up
- Study terminated by sponsor
- Withdrawal by subject
- Death
- Other

The consequence of study withdrawal is that no new information will be collected from the withdrawn patient and added to the existing data or any database.

Millennium or their designee must be notified if a patient is withdrawn from study treatment or from the study. The reason(s) for withdrawal should be documented in the patient’s medical records and eCRF. The investigators must make every reasonable effort to keep each patient on the study until all planned treatments and assessments have been performed. If a patient withdraws from study treatment, every attempt should be made to follow the

patient until death or administrative study closure. Final treatment assessments will be performed before any other therapeutic intervention if possible. Additionally, any planned alternative treatments should be documented on the patient's medical records and CRF.

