5.8.1 Primary Efficacy Endpoint

The primary endpoint of this study is ORR4 per IRF. ORR4 per IRF is defined as the proportion of patients achieving an objective response that lasts at least 4 months (i.e., duration from first response to last response is ≥ 4 months) on study as determined by an IRF. Patients whose first response occurs after the start of subsequent anti-cancer therapy but otherwise meet the primary endpoint criteria will be excluded. For objective response, a patient must achieve a CR or PR. The objective response will be considered maintained for patients with a previous CR who experience recurrent disease (i.e. Relapse) unless the criteria for progressive disease are met. Determination of objective response will be based on a GRS, which consists of skin evaluation (mSWAT assessment) by investigator, nodal and visceral radiographic assessment by IRF, and detection of circulating Sézary cells (MF only) by IRF. Skin evaluation is done at screening, before dosing on Day 1 of Cycles 1, 2, and 3, at the end of every cycle beginning at Cycle 3, EOT, and at post treatment follow-up visits. Radiographic and blood assessments are less frequent due to ethical and logistical considerations.

For patients without nodal or visceral involvement (as determined by baseline CT scans), CT scans will be performed at screening and:

- During the cycle following the first skin response, ideally corresponding to the confirmation of the skin response, and 6 cycles (a minimum or 4 months) after that confirmed skin response.
- If there is a question of new or progressive disease in the LN/viscera

For patients with baseline nodal/visceral disease, CT scans will be performed at screening and:

- At the end of Cycles 3, 6, 9, 12, and 15, and per the follow-up schedule until disease progression
- If there is a question of new or progressive disease in the LN/viscera
- At EOT if the previous CT scan was performed more than 8 weeks before EOT

A blood sample for Sézary cell enumeration in patients with MF will be collected at screening; at the end of Cycles 3, 6, 9, 12, and 15, at EOT, and per the follow-up schedule until progressive disease or study closure.

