5.8.2.1 Analysis on Key Secondary Efficacy Endpoint

5.8.2.1.1 Handling of Missing Assessment and Censoring for Analysis of Progression-free Survival

Disease assessment data should be collected according to the intended schedule of assessment, and the date of PD/response should be assigned based on the time of the first documentation of PD/response regardless of violations or discontinuation of study drug.

For the PFS endpoint, patients who are lost to follow-up, withdraw consent, or those who discontinue treatment due to undocumented PD after the last adequate disease assessment will be censored at the last disease assessment. If death or PD occurs after a missed visit, then the patient is treated as progressed at the date of death or PD. Patients without baseline and/or no sufficient post baseline data for disease assessment and with no death recorded will be censored at the date of randomization. If PD is documented between scheduled visits, then the date of the documented PD is the date of progression. If the patient starts new antineoplastic therapy before PD, then the patient is treated as progressed at the date of assessment at which PD was documented.

The following sensitivity analyses will be performed for PFS to evaluate the robustness of treatment effects. They will be performed on the basis of 1 alteration at a time, not on combined alterations, unless specified otherwise.

- If the PD is documented between scheduled visits, then the date of the next scheduled visit is the date of progression.
- If treatment is discontinued for undocumented PD, then the patient is treated as progressed at the date of last disease assessment.
- Patients who start new antineoplastic therapy before PD will be censored at the date
 of the last disease assessment.
- Patients who start new antineoplastic therapy before PD will be treated as progressed at the date of the last disease assessment.
- If death or PD occurs after more than 1 missed visit, then the patient will also be censored at the last disease assessment before the missed visits.

Another sensitivity analysis will be conducted for PFS per IRF in the ITT population to assess the robustness of the primary analysis's use of most recently available CT scans and

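### The plan does not ensure that anti-CTCL therapy started more than 30 days after the last dose is recorded, although the ORR4 exclusion and two PFS sensitivity analyses depend on it

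*Protocol*

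**What the plan says.** **Collection.** Protocol 7.4.11 states that medications and therapeutic procedures "will be recorded in the eCRF from screening through 30 days after the last dose of study medication". The Schedule of Events row for concomitant medications and procedures agrees: "Recorded from screening through 30 days after the last dose of study drug". The EOT visit is itself set at 30 days (±2) after the last dose. The visible entries in the posttreatment follow-up column cover disease status and survival, physical examination, mSWAT and photographs, CT, Sézary cells, biopsies, questionnaires and healthcare utilization. None is for later anti-CTCL therapy.

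**Follow-up.** Protocol 4.3: "Posttreatment assessments of disease response will be conducted every 12 weeks for a minimum of 24 months after EOT", then every 6 months, until progression or study closure. Starting another treatment does not end these assessments. Protocol 7.7 keeps patients who stop for reasons other than progression in the same schedule.

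**Analysis rules.** For the primary endpoint, SAP 5.8.1 says: "Patients whose first response occurs after the start of subsequent anti-cancer therapy but otherwise meet the primary endpoint criteria will be excluded". For PFS, SAP 5.8.2.1.1 lists two sensitivity analyses on new therapy. One censors such patients. The other reads: "Patients who start new antineoplastic therapy before PD will be treated as progressed at the date of the last disease assessment".

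**Other mentions of later therapy.** Protocol 7.8, on patients who withdraw, says that "any planned alternative treatments should be documented on the" medical records and CRF. Protocol 4.3 says that for control completers "initiation of subsequent standard-of-care therapy should be discussed with the study sponsor", and that for patients who complete 16 cycles "access to brentuximab vedotin may be permitted in accordance with local regulatory requirements and at the joint discretion of the sponsor and investigator".

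**The concern.** The SAP asks whether, and when, a patient started other therapy during a period in which the protocol has stopped asking sites to record it.

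The primary endpoint is where this matters most. Under SAP 5.8.1, GRS at posttreatment visits still counts. Take a patient who stops for toxicity without a response and without PD, starts phototherapy 45 days after the last dose, responds at a 12-week visit and holds the response for 4 months. SAP 5.8.1 means to keep this patient out of the responders, but the record that the protocol prescribes would not show the phototherapy.

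For PFS, the two sensitivity analyses exist to show whether later therapy drives the result. If therapy begun after the 30 days is not recorded, those patients are handled exactly as in the primary analysis, and agreement between the analyses says less than it appears to.

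**Working it through.** No figure in the plan is in dispute, so the main check sets each SAP rule that mentions later therapy against the recording window.

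| SAP rule | Needs later-therapy data after EOT? | Reason |
|---|---|---|
| ORR4 exclusion (5.8.1) | Yes | First response must be ordered against start of therapy |
| PFS sensitivity, censor (5.8.2.1.1) | Yes | Must know that therapy began before PD, and which assessment came last before it |
| PFS sensitivity, event (5.8.2.1.1) | Yes | Same |
| Primary PFS (5.8.2.1.1) | No | Uses the documented PD date despite new therapy |
| DOR, duration of skin response (5.8.3.1) | No | Same handling |
| EFS (5.8.3, 5.8.3.1) | No | Treatment discontinuation is already an event |

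Three rules remain.

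**When recording ends.** With full treatment in the control arm: (48 × 7 + 30)/30.4375 = 12.0 months after first dose. With 16 cycles of brentuximab vedotin the last dose falls at week 45: (45 × 7 + 30)/30.4375 = 11.3 months. Patients who stop early leave the window sooner.

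**How much PFS information falls later.** Inputs: medians of 9 and 6 months (SAP 5.8.2.1.2), 62 per arm, 24 months' enrolment and analysis at about 34 months (Protocol 4.3). Assumptions: exponential PFS and uniform accrual. The model first has to agree with the SAP's projection of about 101 events. It gives 48.9 + 55.4 = 104 without dropout, and 98 to 102 with 10% loss spread over 12 to 34 months, so it does.

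- Progression-free at 12.0 months: 0.5^(12.02/9) = 40% and 0.5^(12.02/6) = 25%.
- Expected events after 12.0 months, as n × average over follow-up f of [S(12.0) − S(f)] for f > 12.0: 11.6 + 9.0 = 21 of 104.
- If recording ended at 6 months for everyone, 50 of 104; at 4 months, 65 of 104.

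These figures show how much follow-up lies outside the window. They do not count patients who start therapy.

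**Sensitivity of ORR4, by assumption.** Planning rates of 70% and 40% at 62 per arm correspond to about 43 and 25 responders, a difference of 18/62 = 29.0 points. Let k control patients be wrongly kept as responders. Power is the normal approximation to the unstratified two-sided test at 0.05, for 70% against 40% + k/62:

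Φ{[Δ√62 − 1.96√(2p̄(1−p̄))]/√(p₁(1−p₁)+p₂(1−p₂))}

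| k | Difference in counts, points | Approximate power |
|---|---|---|
| 0 | 29.0 | 93% |
| 1 | 27.4 | 90% |
| 3 | 24.2 | 82% |
| 6 | 19.4 | 64% |

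A patient wrongly kept in the brentuximab vedotin arm moves the difference 1.6 points the other way. The documents give no basis for choosing k in either arm.

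**The case against.** The strongest reply is that 7.4.11 governs concomitant medication and does not say that nothing else is collected. The eCRF and Study Manual are not in the documents, Protocol 7.4.24 on healthcare utilization is redacted, and the disease status/survival row does not list its fields. A subsequent-therapy page may exist. That stands as a limit: the supportable claim is that the visible protocol does not ensure the data. It does not remove the point, because sites work to the protocol and the only window it states ends at 30 days. SAP 5.10.2 describes the utilization data as hospitalization, missed days and caregiver information, with no treatment dates. SAP 5.7.1 tabulates medications to the end of an on-study period that it does not define.

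A reader might infer that the three rules cannot be applied at all, or that the PFS sensitivity analyses would simply reproduce the primary result. Neither follows. Therapy started within 30 days of the last dose is recorded and would alter both analyses, and 7.8 puts planned alternative treatments on the CRF at withdrawal. A plan is not a start date, however, and it misses decisions made later. The sponsor contact in 4.3 covers only patients who complete the course and names no data field.

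A reader might also infer that brentuximab vedotin given again after the course escapes every rule because it is not new therapy. The ORR4 rule speaks of subsequent therapy, which such treatment fits. In the PFS rules, what counts as new is undefined.

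Nor do the documents show a clear difference in risk between arms. Section 4.3 says that control completers should discuss standard-of-care therapy, and Protocol 1.4.2.2 calls methotrexate a standard of care, so a return to the same drug is possible in the control arm too.

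Protocol 6.5 prohibits other active treatment during the study, but 7.4.11 describes that list as applying during study treatment, and 4.3 foresees later therapy.

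**Conclusion.** The point holds for three rules: the ORR4 exclusion and the two PFS sensitivity analyses on new therapy. For these, a stated recording window conflicts with stated analysis rules. It does not reach primary PFS, DOR, duration of skin response or EFS.

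The size is unknown. For ORR4, the patients at risk had no response before other therapy, stopped without PD, started that therapy more than 30 days after the last dose, and then responded for at least 4 months. Patients who first responded on study drug are outside the rule. A reader might take the 40% and 25% still progression-free at 12 months as the affected patients. They are not: those shares describe who remains under follow-up, and many will be earlier responders. The firm quantity is 1.6 points of ORR4 per misclassified patient; the power figures hold only for the assumed counts in the control arm.

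Timing also limits the effect on the final analysis, which comes 10 months after the last enrolment, before late-enrolled patients can leave the window after full treatment. The updated analysis, after 24 months of posttreatment follow-up, is more exposed. This is a cheap improvement worth making, and the conclusion would fall away if the eCRF already has such a page.

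**What to change.** 1. In Protocol 7.4.11 and the follow-up column of the Schedule of Events, add an item for subsequent anti-CTCL therapy. Record the type (systemic, radiotherapy, phototherapy, skin-directed) and start date at follow-up contacts already scheduled, until PD per IRF or study closure. If the eCRF already collects this, say so in both places.
2. In SAP 5.8.1 and 5.8.2.1.1, define the trigger as any anti-CTCL therapy started after the last protocol dose, including study drugs given outside the protocol course, and name the data field.

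SAP 5.8.3.1 needs no change. The cost is one follow-up eCRF page, a sentence or two in each document and a small amount of extra site data entry. No visits are added.

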7.4.12 Adverse Events

Monitoring of AEs, serious and nonserious, will be conducted throughout the study as specified in the [Schedule of Events](#). Refer to Section 10 for details regarding definitions, documentation, and reporting of pretreatment events, AEs, and SAEs. Changes in the severity of events relating to peripheral neuropathy will be recorded as described in Section 10.3.

7.4.13 Enrollment

A patient is considered to be enrolled in the study when randomized to a treatment arm.

Procedures for completion of the enrollment information are described in the Study Manual.

7.4.14 ECG

A 12-lead electrocardiogram (ECG) will be administered at the time points specified in the [Schedule of Events](#).

7.4.15 Clinical Laboratory Evaluations

Clinical laboratory evaluations must be performed centrally at screening and per the Schedule of Events. For decisions regarding eligibility (values required within 4 days of randomization) and treatment, local hematology and chemistry results may be used. Sézary cell results must be available from the local lab to determine eligibility and treatment decisions. Handling and shipment of clinical laboratory samples will be outlined in the study manual.

Brentuximab vedotin (SGN-35)

Clinical Study Protocol C25001 Amendment 5, EudraCT: 2010-024215-14

Clinical Chemistry, Hematology, and Urinalysis

Blood samples for analysis of the following clinical chemistry and hematological parameters and urine samples for urinalysis will be obtained as specified in the [Schedule of Events](#).

Hematology

- Hemoglobin
- Hematocrit
- Platelet count
- Leukocytes with differential
- Neutrophils (absolute neutrophil count [ANC])

Serum Chemistry

- BUN
- Creatinine
- Bilirubin (total)
- Urate
- Lactate dehydrogenase (LDH)
- Phosphate
- Gamma glutamyl transferase (GGT)
- Albumin
- Alkaline phosphatase (ALP)
- Aspartate aminotransferase (AST)
- Alanine aminotransferase (ALT)
- Glucose
- Sodium
- Potassium
- Calcium
- Chloride
- Carbon dioxide (CO₂)
- Magnesium
- Amylase
- Lipase

Urinalysis

- Turbidity and Color
- pH
- Specific gravity
- Protein
- Ketones
- Bilirubin
- Blood
- Nitrite
- Urobilinogen
- Glucose
- Leukocytes

Lipid Panel

- Total Cholesterol
- HDL
- LDL
- Triglycerides

Thyroid Panel

- TSH
- Free T3
- Free T4

Immune Reconstitution Assessments

- Lymphocytes counts
- Phenotypic T, B, and NK cell subsets:
 - CD4⁺ T cells counts
 - CD8⁺ T cells counts
 - CD8/CD4 ratio
 - CD19⁺ B cells counts
- NK cells (CD3⁻ CD56 CD16⁺ vs. CD3⁻ CD56 CD16⁻)

Other

- Hemoglobin A1C

7.4.16 Disease Assessment

A GRS of complete response (CR), partial response (PR), stable disease (SD), progressive disease (PD), and relapse will be determined based on sequential tumor burden assessments of body compartments (skin, lymph nodes, viscera, and blood for MF patients) as further described below. For the purpose of disease assessment in the control arm, a period of 3 weeks (21 days) is equivalent to 1 cycle.

Response will be determined by a composite assessment of total tumor burden:

- Cutaneous disease (mSWAT) (Section [7.4.17.1](#))
- Lymph node involvement (Section [7.4.17.2](#))
- Visceral involvement (Section [7.4.17.2](#))
- Blood (MF patients only) (Section [7.4.17.3](#))
 - Sézary cells will be enumerated by morphology and immunophenotyping

7.4.17 Response Assessments

7.4.17.1 Cutaneous Disease Response Assessment

7.4.17.1.1 mSWAT

The mSWAT assessment tool will be used for MF and pcALCL and will be performed as specified in the Schedule of Events.

Brentuximab vedotin (SGN-35)**Clinical Study Protocol C25001 Amendment 5, EudraCT: 2010-024215-14**

The mSWAT score calculation method and skin lesion definitions for MF and pcALCL are provided in [Table 7-1](#).

Table 7-1 Modified Severity Weighted Assessment Tool

Body Region	% BSA in Body Region	Assessment of Involvement in Patient's Skin		
		Patch ^a	Plaque ^b	Tumor ^c
Head	7			
Neck	2			
Anterior trunk	13			
Arms	8			
Forearms	6			
Hands	5			
Posterior trunk	13			
Buttocks	5			
Thighs	19			
Legs	14			
Feet	7			
Groin	1			
Subtotal of lesion BSA				
Weighting factor		x1	x2	x4
Subtotal lesion BSA x weighting factor				

mSWAT score equals summation of each column line.

Abbreviations: BSA = body surface area; mSWAT = modified Severity Weighted Assessment Tool.

- a Any size lesion without induration or significant elevation above the surrounding uninvolved skin; poikiloderma may be present.
- b Any size lesion that is elevated or indurated; crusting, ulceration, or poikiloderma may be present.
- c Any solid or nodular lesion \geq 1 cm in diameter with evidence of deep infiltration in the skin and/or vertical growth.

The mSWAT score will be calculated as follows:

$$\begin{aligned}
 & \text{Sum of \%TBSA from all body regions affected by patches x severity-weighting factor of 1} \\
 & + \text{Sum of \%TBSA from all body regions affected by plaques x severity-weighting factor of 2} \\
 & + \text{Sum of \%TBSA from all body regions affected by tumors x severity-weighting factor of 4} \\
 & = \text{Total mSWAT (maximum score = 400)}
 \end{aligned}$$

Brentuximab vedotin (SGN-35)

Clinical Study Protocol C25001 Amendment 5, EudraCT: 2010-024215-14

Figure 7-1 presents the mSWAT % of total body surface area for the 12 main body areas to assess disease burden in MF and pcALCL.^(60,61) The body is divided into 12 regions with preassigned % of total body surface area (TBSA) based on methodology used to assess burns.⁽⁶²⁾ The extent of skin disease is assessed for each region and quantified using the patient's palm as a "ruler" to measure the % of TBSA involvement within each region:

Patient's palm with 4 fingers and including the thumb, and measured from wrist to fingertips, is approximately 1% of TBSA.

Figure 7-1 mSWAT % Total Body Surface Area (TBSA) for 12 Main Body Areas

[figure not shown]

Table 7-2 Response in Skin

Response	Definition
Complete response (CR)	100% clearance of skin lesions ^a
Partial response (PR)	50%-99% clearance of skin disease from baseline No new tumors in patients without tumors at baseline (MF) No new tumors (pcALCL)
Stable disease (SD)	< 25% increase to < 50% clearance in skin disease from baseline No new tumors in patients without tumors at baseline (MF)
Progressive disease (PD) ^b	≥ 25% increase in skin disease from baseline, or Loss of response: in those with CR or PR, increase of skin score of greater than the sum of nadir plus 50% baseline score, or New tumors in patients without tumors at baseline (MF)
Relapse	Any disease recurrence in those with complete response

Response criteria for MF are per Olsen 2011,⁽⁴⁾ and for pcALCL per Kempf 2011.⁽¹⁾

Abbreviations: CR = complete response; PR = partial response; SD = stable disease; PD = progressive disease.

a A biopsy of normal appearing skin is unnecessary to assign a complete response. However, a skin biopsy should be performed on a representative area of the skin if there is any question of residual disease (persistent erythema or pigmentary change) where otherwise a complete response would exist. If histologic features are suspicious or suggestive of mycosis fungoides/Sézary syndrome, the response should be considered a partial response only.

b Whichever criterion occurs first.

